#### **6.5. Laboratory Tests**

All laboratory test results may be obtained as archival material from the patient’s chart or should be collected as part of the standard of care during screening. Maximum acceptable intervals between the date of collection of laboratory results and GpR 2 registration (date of initial screening visit) will be specified on the data collection form. The blood collection date of the laboratory tests must be

recorded on the data form. The etiologic tests: anti-nuclear antibody (ANA), high sensitivity C-reactive protein (hs-CRP), sedimentation rate (ESR); complete blood count (white blood cell count (WBC), red blood cell count (RBC), hemoglobin, hematocrit, platelet count); comprehensive metabolic panel (sodium, potassium, chloride, carbon dioxide, calcium, BUN, creatinine, glucose, and liver panel including total protein, albumin, total bilirubin, aspartate aminotransferase (AST), alanine aminotransferase (ALT), alkaline phosphatase); thyroid stimulating hormone (TSH); vitamin B12, 25-hydroxy vitamin D level, lipid profile (total cholesterol, high density lipoprotein (HDL), low density lipoprotein (LDL), triglycerides) and hemoglobin A1c are required once as part of screening. **HbA1c will be required at each follow-up visit for diabetic participants.**

#### **6.6. Plasma, serum, and DNA for banking**

Fasting blood collection for plasma and serum banking will be banked in the NIDDK Biosample Repository. Blood will be collected at the screening/enrollment visit and yearly thereafter on all patients enrolled in the Gastroparesis Registry 2. Blood collection for DNA extraction and banking will be performed during screening. The banked samples will be used for specific Gastroparesis Registry 2 research questions and other GpCRC ancillary studies. Standardized methods for plasma, serum, and DNA processing that allow for maximal preservation of banked specimens and storage in designated -70 degrees C freezers will be applied across all clinical centers and at the NIDDK central repositories (see GpR 2 Standard Operating Procedures (SOP) I: Clinical Center Operations).

#### **6.7. Specific tests**

##### **6.7.1. Gastric emptying of solids and liquids**

The gastric emptying test for enrollment into GpR 2 will be a combined simultaneous gastric emptying of solids and liquids using the Egg Beaters® meal protocol. Liquid egg white will be labeled with Tc-99m and water labeled with Indium-111. The liquid emptying is measured in the presence of the solid meal. An allergy to eggs is a contraindication to this test.

Patients are instructed to stop medications that could affect gastrointestinal motility for the 3 days prior to the gastric emptying scintigraphy and to come for the test in the morning after fasting overnight with nothing to eat after midnight, (an 8 hour fast). The patient fills out the Pagi-SYM questionnaire assessing symptoms over the past 2 weeks. Diabetic patients must have a fasting blood glucose level checked within the hour prior to consumption of the meal.

Gastric emptying scintigraphy is performed using a standard low-fat, Egg Beaters® (egg white) meal to measure solid emptying. The Egg Beaters® are radiolabeled with 0.5 -1 microcurie technetium-99m sulfur colloid and served with two pieces of white bread and strawberry jam. The meal has a caloric value of 255 kcal (nutritional composition: 72% carbohydrate, 24% protein, 2% fat, and 2% fiber). The participant is instructed to ingest the meal within 10 minutes. Each participant then drinks 120 mL of water containing 125 microcurie (4.6 MBq) of Indium 111-DTPA (diethylene triamine pentacetic acid) for the measurement of liquid gastric emptying and small bowel and/or colon transit.

For quality control, the staff technologist records how long it takes the participant to consume the meal and how much they consume. The patient should ingest the whole meal. If the patient cannot eat the entire meal, at least 50% of each component should be consumed for the test. If the patient vomits part of the meal at any time during the test, this should be indicated on the report. Clinically the study is non-diagnostic for gastroparesis if normal and only a small portion is eaten. If gastric emptying is delayed for a small meal ingested it can, however, indicate delayed gastric emptying.

Combined technetium-99m and Indium-111 imaging begins immediately after consumption of the liquid and is repeated at 30 min, 1 hour, 2 hours, 3 hours, and 4 hours to record gastric emptying of liquids and solids. If small bowel transit is to be obtained, then In-111 imaging is also performed at 5 and 6 hours after meal ingestion. Between all image sets, the participants are permitted normal quiet activity (e.g., reading, watching television and/or videos) in the standing or sitting position.

*Note: If gastric emptying of liquids is performed on a separate day than gastric emptying of solids, the patient consumes an unlabeled Egg Beaters® meal (Egg Beaters®, bread, jam) with the radiolabelled water.*

Analysis of the gastric emptying data is performed. Images are recalled from a computer disc and analyzed to determine gastric counts. Regions of interest (ROIs) are manually drawn around the total stomach at each time interval. A geometric mean of the anterior and posterior values is used to correct for depth changes (geometric mean counts = square root [anterior counts × posterior counts]) and counts are corrected for radioisotope decay.

Normal values for gastric emptying scintigraphy and small bowel transit have been established in earlier studies using healthy volunteers. Gastric retention of Tc-99m > 60% at 2 hours and/or > 10% at 4 hours was considered evidence of delayed gastric emptying of solids. Rapid gastric emptying of solids was defined as < 35% retention of Tc-99m at 1 hour. Delayed gastric emptying of liquids in the presence of solids is greater than 50% retention of In-111 at 1 hour emptying, a value representing the mean plus 2 standard deviations of values derived from 20 normal subjects from prior studies using a similar solid and liquid meal.

### 6.7.2. Regional gastric emptying

The gastric emptying tests will be performed at the local centers and the images saved. The centers will need to de-identify the patient information using available software and send the images in DICOM format to Temple University Nuclear Medicine for regional gastric emptying scintigraphy analysis. (Details will be in the GpR 2 Standard Operating Procedures (SOP) I: Clinical Center Operations manual.)

*Analysis:* Gastric emptying scintigraphies using the standardized meal with 4 hour imaging will be analyzed for proximal, distal, and total gastric retention in patients undergoing GES for clinical evaluation. Regional gastric emptying of the proximal and distal stomach will be analyzed by drawing regions representing the proximal and distal portions of the stomach. Proximal gastric retention will be expressed as the percent of radioactivity in the proximal stomach calculated by dividing the corrected counts in the proximal stomach at each time period by the total counts in the total stomach at time 0. Distal gastric retention in the distal stomach will be expressed as the percent of radioactivity in the distal stomach calculated by dividing the radioactivity count in the distal stomach at each time period by the count in the total stomach at time zero. We will look at the regional emptying curves: % in that region at specific times, and time to maximum in distal stomach, and slope of emptying in each region.

### 6.7.3. Wireless motility capsule and EGG

A wireless motility capsule, SmartPill® measures gastric emptying, small bowel transit time (SBTT), and colon transit time (CTT) and is approved for the evaluation of presumed gastroparesis and slow transit constipation. The SmartPill® has pH, pressure, and temperature sensors to quantify gastric, small bowel, and colon transit and contractility. SmartPill® showed good correlation with gastric scintigraphy (R=0.73) in 87 controls and 61 patients with prior gastroparesis diagnoses.

SmartPill® sensitivities and specificities (65% and 87%) were comparable or superior to 4 hour scintigraphy (44% and 93%) and supported equivalency of SmartPill® with scintigraphy methods advocated by consensus guidelines. In constipated patients, SmartPill® colon transits showed good correlations with radioopaque marker studies. In retrospective analyses, SmartPill® testing gave many new diagnoses in 86 patients with symptoms in the upper or lower gut including detecting slow transit constipation or small bowel dysmotility in patients thought to have only gastroparesis. This emphasizes the effectiveness of SmartPill® to characterize regional and generalized motor disorders in one test.

*Test procedure criteria:* Patients must be able to stop proton pump inhibitors for 7 days, and stop histamine 2 antagonists, prokinetics, narcotics, anticholinergics, and cannabinoids for 3 days. The SmartPill® is contraindicated in patients with bezoars (retained liquid or poorly organized solids are permitted), dysphagia, prior gut lumen surgery (prior Nissen fundoplication is permitted), known strictures, prior inflammatory bowel disease, prior diverticulitis, chronic frequent NSAID use, and cardiac medical devices (gastric stimulators, insulin pumps, continuous glucose monitors are permitted).

***Patient preparation required for the SmartPill® with EGG test***

- 1) Patient will stop proton pump inhibitors for 7 days prior to visit 2;
- 2) Patient will stop histamine 2 antagonists, prokinetics, narcotics, anticholinergics, constipation medications (over the counter laxatives, isotonic polyethylene glycol (PEG) electrolyte preparations (e.g. MiraLax), and prescription laxatives (e.g. lubiprostone), and cannabinoids for 3 days prior to the visit; and
- 3) Patients will continue to abstain from prokinetics, proton pump inhibitors, and ‘over the counter’ laxatives, isotonic PEG electrolyte preparations (e.g. MiraLax), and prescription laxatives (e.g. lubiprostone) after ingesting the SmartPill® until they return for the follow-up visit in 4-7 days.
- 4) Patients will not swallow the SmartPill®, if they have a history of bezoars (retained liquid or poorly organized solids are permitted), significant dysphagia, prior gut lumen surgery (except fundoplication), known strictures, prior inflammatory bowel disease, and cardiac medical devices (gastric stimulators, insulin pumps, continuous glucose monitors are permitted).

***Data to be Collected:***

Survey Instruments: PAGI-SYM, Rome III questionnaire, and visual analog symptom (VAS) scales: Patients will be instructed to put a cross in 10 cm lines reflecting symptom severity of nausea, fullness, hunger, pain, discomfort, bloating, and distention. VAS data sheets will be completed before SmartPill® ingestion, and at 10, 20, 30, 60, and 90 minute time periods after ingestion of the SmartPill®.

***Items needed for the test:***

The SmartPill® data capture system and receiver, a SmartPill® capsule, a SmartBar®, a cup that has a 50mL measured mark for water during meal ingestion (at least 100mL of water is needed for the test), 3 EGG leads, a dedicated quiet area for the EGG recording, a reclining chair, a blanket, 3CPM EGG equipment and software, and a laptop or computer with the SmartPill® analytic software are required for this test.

***Test protocol:***

The Study Physician will complete the Baseline Medical History and Physical Examination, if not previously performed. On the day of the test, patients are instructed to come in the morning after

fasting overnight with nothing to eat after midnight - an 8 hour fast. Women of child-bearing potential will have urine pregnancy tests. Diabetics will have a finger stick testing of blood glucose and if  $>270$  mg/dL, the study will be rescheduled. Prior to testing, participants will complete the PGI-SYM questionnaire assessing symptoms over the past 2 weeks and the Rome III questionnaire. The SmartPill® will be activated and calibrated.

To streamline the number of visits for each patient, SmartPill® ingestion will be performed on the same day as EGG testing with the SmartBar® as the standard test meal. Baseline symptoms prior to EGG recording will be obtained using visual analog scales (VAS) for stomach fullness, hunger, nausea, bloating, and abdominal discomfort. The patient will recline in a chair at a 30-45 degree angle in a comfortable position. A fasting EGG will be performed for 15 minutes before SmartBar® ingestion.

After the baseline EGG recording is completed, the patient will begin the standard solid meal test by sitting up in the chair and ingesting one SmartBar® in a 10 minute period with 50 mL of room temperature water. It is expected that 100% of the bar will be ingested. The percentage of the SmartBar® that is consumed will be documented. After the SmartBar® is consumed; the SmartPill® will be ingested with another 50 ml of water and another visual analog scales symptoms sheet will be completed. The subject will then recline in the 30-45 degree position that they were in for the fasting baseline condition. The electrodes will be checked to verify that they are well adhered to the skin and the respiratory belt will be checked to verify it is snug before starting the EGG recording for the 90 minute postprandial period. Visual analog scales for stomach fullness, hunger, nausea, bloating, and abdominal discomfort will be completed at the 10, 20, 30, 60, and 90 minute time periods after ingestion of the SmartPill®. The patient may get out of the chair to stretch for 2 minutes at 30 and 60 minutes if necessary. At the 90 minute point the test is completed and the electrodes are removed. (Further details of the EGG recording and questionnaires will be in the SOP.)

Patients will be permitted to leave the study center after completion of the 90 minute EGG recording after SmartPill® ingestion. Study participants will leave with instructions to:

- 1) Remain fasting for 6 hours after SmartPill® ingestion; thereafter resume a normal diet; maintain a diary recording times of meal ingestion, bowel movements, and sleep; and keep the receiver in close proximity for 4-7 days. An event marker on the receiver will be depressed for diary entries.
- 2) Complete all remaining questionnaires for GpR 2: food questionnaire, nausea and vomiting questionnaire, neuropathy profile; abdominal pain questionnaire, state trait anxiety
- 3) Continue to abstain from prokinetics, proton pump inhibitors, and 'over the counter' laxatives, isotonic PEG electrolyte preparations (e.g. MiraLax), and prescription laxatives (e.g. lubiprostone) after ingesting the SmartPill® until they return for the follow-up visit
- 4) Return fasting for a follow-up visit 4-7 days after SmartPill® ingestion to return the receiver, questionnaires, and diaries for analysis.

SmartPill® expulsion will be queried and a second follow-up will be scheduled if needed. Standard protocols will be activated if SmartPill® retention is suspected after 14 days.

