**Screening and Enrollment:**

- Enrollment must occur within 16 weeks of informed consent and registration
- Follow-up visits will occur at 24, 48, 72, 96, 120, 144, 168, 192, 216, and 240 weeks

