data forms. The eligibility check task may be run at any time, and there is no limit on the number of times it may be run. The output from the task will list the eligibility checks that the patient has failed and a summary finding that the patient is eligible or ineligible for enrollment into the study. Thus staff can use this task to identify the items that still need to be completed, keyed, or verified after data from screening visits are keyed. The date of enrollment is the time zero for reckoning all follow-up visits (i.e., all follow-up visits are scheduled at specific times measured from the date of enrollment). On the day of enrollment the data system will generate a visit windows schedule for the patient; this schedule will indicate the ideal date for each follow-up visit, as well as the time window around the ideal date during which the follow-up visit may be done and the data collected at the visit may be used in the study.

*Note: Some patients may not be able complete all the study procedures. For instance, some may not have the liquid phase gastric emptying scintigraphy performed due to center specific logistical issues or some may not be able to swallow the SmartPill® or some may not complete EGG with SmartBar or water load testing. These patients may still be enrolled.*

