#### *Week 48 visits (2 separate days)*

The week 48 follow-up visits require 2 separate days of testing and participants will come fasting for each day of testing. Medications that delay gastric emptying such as narcotic analgesics and medications that enhance gastric emptying such as prokinetics will be stopped for 3 days prior to the visits. A follow-up medical history (medication changes/additions, symptom exacerbations or interventions, surgeries, hospital admissions, new diagnoses of co-morbidities, complications of

interventions such as infections, documentation of any additional GI tests performed as part of standard of care), and physical examination, including weight, height, and waist/hip circumference, blood pressure, heart rate, respiratory rate and body temperature will be performed.

Participants will have a repeat 4 hour gastric emptying scintigraphy test of solids only using the Egg Beaters® with toast and jam will be performed. Medications taken during the past week will be recorded. For diabetic patients, a fasting blood glucose level must be checked within the hour prior to the gastric emptying test to ensure it is less than 270 mg/dL. Patients will also complete the PGI-SYM questionnaire immediately prior to the gastric emptying test.

On a second day, the autonomic function testing and a repeat EGG with water load test will be performed. On the morning of the EGG and water load satiety test, the patient will arrive fasting. Patients may take their usual medications with a small amount of water (up to 4 oz) up to two hours prior to the study, but should refrain from coffee, tea, or juice. After arriving to the clinic, the patient's blood glucose level must be checked to ensure it is less than 270 mg/dL. If the patient's blood glucose level is greater than 270 mg/dL the EGG and water load satiety test must be rescheduled for another day.

Draw 10 mL of blood for serum banking and 10 mL of blood for plasma banking at the NIDDK Biosample Repository. Blood will be drawn to obtain HbA1c values for patients with diabetes. Participants will complete the following additional questionnaires:

- Patient Assessment of Upper Gastrointestinal Disorders - Quality of Life (PAGI-QOL)
- Beck Depression Inventory (BDI-II)
- State Trait Anxiety Inventory (STAI)
- Neuropathy Total Symptom Score (NTSS-6)
- Block 2005 Food Frequency Questionnaire
- Block Energy Expenditure Survey

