**Autonomic function testing:** Autonomic testing in this study uses an electrocardiogram to measure cardiac electrical activity. There may be some discomfort when removing the recording pads on the chest. In addition, autonomic function testing takes blood pressure and pulse when the patient changes from a lying down to standing position. Some patients may develop lightheadedness when standing. If this happens, the patient will promptly lie down.

**Gastric emptying scintigraphy test:** The gastric emptying of solids and liquids for enrollment into the registry is performed for the patient's clinical evaluation. In this study, a repeat gastric emptying

scintigraphy of solids only is performed 48 weeks after enrollment. *Radiation Exposure.* The effective dose to a patient per test from the 0.5 -1 microcurie Tc-99m egg meal is estimated to be 37-53 millirem (adult male and adult female, respectively), assuming normal transit times. This is below the total average annual dose a person in the United States receives from natural background radiation. Natural annual background exposure averages 300 millirem (3 mSv). Although no immediate harmful effects are expected, there is a very small, theoretical (that means not proven) long-term health risk from this small amount of radiation exposure. The amount of radiation to which participants may be exposed to could be higher or lower than this value depending on their body weight or size.

**General risks:** The condition of the patient may or may not get better or may become worse while they are in the Gastroparesis Registry 2 study. This is not a treatment study. During the study, patients will still be getting clinical care by their physician.

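### No pregnancy test is listed before the week-48 Tc-99m scan done for the study; the protocol's only one precedes a baseline procedure without radiation

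*Protocol*

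**What the plan says.** Protocol section 6.7.3, under its test protocol for the capsule and EGG visit, requires that "Women of child-bearing potential will have urine pregnancy tests". The procedure it precedes is a nutrient bar, an EGG recorded from skin electrodes, and a swallowed capsule that "has pH, pressure, and temperature sensors to quantify gastric, small bowel, and colon transit and contractility". The list of measures in the Design synopsis marks this test as baseline only, and the 11.2 schedule shows it only at screening.

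For week 48, section 6.3 states: "Participants will have a repeat 4 hour gastric emptying scintigraphy test of solids only". Section 9.1 says that the enrollment scan is done for the patient's clinical evaluation, and then that in this study a repeat "scintigraphy of solids only is performed 48 weeks after enrollment". It gives the effective dose from the Tc-99m meal as 37–53 millirem per test (adult male and adult female respectively), against an annual background of 300 millirem.

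Section 6.3 also fixes what must happen before the week-48 scan, including a metabolic check: "For diabetic patients, a fasting blood glucose level must be checked within the hour prior to the gastric emptying test". It lists no pregnancy test.

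**The concern.** The protocol requires a pregnancy test before a procedure without radiation and lists none before the one radionuclide procedure that it adds for study purposes. Women of child-bearing potential are likely to form much of this cohort: section 1.1 describes a disorder mainly of young women, with a 4:1 female-to-male ratio and an average age of 34. Nausea and vomiting, the leading symptoms in Table 1 (92% and 84%), can also be early signs of pregnancy, so symptoms alone are a weak prompt to suspect one.

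What is at stake is participant safety. A site following the listed steps exactly could give a radiolabelled meal, for a study test, to a woman who does not know that she is pregnant. No estimate, power figure or inference depends on this point.

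**Working it through.** The check is mainly a reading of every place where a safeguard could stand.

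| Place in protocol | Content relevant to the week-48 scan | Pregnancy test or rule? |
|---|---|---|
| 5.2 Exclusion criteria | Pregnancy not listed; criteria apply only at entry | No |
| 6.2 Gastric emptying scintigraphy (screening) | Medication stop, medication record, glucose in diabetics, symptom questionnaire | No |
| 6.3 Week 48 visits | Fasting, 3-day medication stop, medication record, glucose in diabetics, symptom questionnaire, history and examination | No |
| 6.7.1 Scan procedure | Meal, labelling and imaging; one contraindication: "An allergy to eggs is a contraindication to this test" | No |
| 6.7.3 Capsule and EGG | Baseline visit only, no radionuclide | **Yes** |
| 9.1 Risks | Dose and background comparison | No |
| 11.2 and 11.3 schedules | Scan marked at week 48; no pregnancy-test row | No |

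Count: one pregnancy test in the protocol, at the baseline capsule visit; none before the week-48 scan.

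**Can the baseline test serve for week 48?** The synopsis states: "Enrollment must occur within 16 weeks of informed consent and registration". Section 6.2 counts follow-up visits from the enrollment date. The baseline test can therefore fall from 0 to 16 weeks before enrollment:

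- Age of result at the week-48 target date = 48 + (0 to 16) = 48 to 64 weeks.

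Even the lower end is longer than a pregnancy lasts, so the baseline result says nothing about pregnancy on the day of the scan.

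**Did every eligible woman have the baseline test?** Not necessarily. The note at the end of section 6.2 says that "some may not complete EGG with SmartBar or water load testing. These patients may still be enrolled". It does not say that such patients miss the visit, so this shows only that a baseline test is not guaranteed. The finding does not depend on it.

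**Size of the exposure as stated in 9.1:**

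- 37 / 300 = 12.3% of annual background
- 53 / 300 = 17.7% of annual background

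These are adult effective doses. The protocol gives no fetal dose, so the percentages show only that the stated exposure is small. The documents give neither a pregnancy rate nor the number of women of child-bearing potential expected at week 48, so the number exposed cannot be calculated.

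**The case against.** The strongest reply is that this is silence and not an error: no sentence is wrong, and no two sections conflict. Scans are performed at the clinical centers, which follow local review-board rules and Good Clinical Practice. Much procedural detail is deferred to SOPs, and the consent forms are not available here. Any of these may already require a pregnancy test. The week-48 medical history and examination could also reveal a known pregnancy.

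It is also fair to say that the protocol never explains why it tests before the capsule. That test may have its own rationale for an ingested device, so the contrast does not prove that the authors meant to test before scintigraphy and forgot. Section 6.7.1 opens by describing the enrollment scan, so its silence is weaker evidence than that of 6.3, 9.1 and 11.2. The stated dose is low.

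Most of this limits the weight of the point without removing it. Actual practice may be safer than the text, but none of the sections that defer to SOPs or local rules says that pregnancy screening is covered there. The protocol itself sets the pre-scan checks for week 48, down to a timed glucose measurement, so a reader would take the list as complete. A history and examination are not designed to find an unrecognised pregnancy. Pregnancy testing is a safety procedure and would not be expected in a statistical analysis plan.

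**Conclusion.** The concern holds. The protocol lists one pregnancy test, before a baseline procedure without radiation, and none before the week-48 Tc-99m scan that it adds for study purposes. By then the baseline result is 48 to 64 weeks old and uninformative.

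The weight is moderate: this should be corrected, but no harm has been shown. The stated adult dose is 37–53 millirem, below annual background, and the number of pregnancies affected is unknown. The conclusion concerns the protocol text only and assumes that no SOP, consent form or local rule outside it fills the gap; those documents were not available.

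**What to change.** In section 6.3, under the week-48 visits, require a urine pregnancy test in women of child-bearing potential before the scan, alongside the glucose check. If it is positive, omit the scan, record it as not done because of pregnancy, and continue all other follow-up. Add a row to the 11.2 schedule at week 48 and state the rule in 9.1 next to the radiation dose. In 6.7.1 a short cross-reference is enough, making clear that the requirement applies to the week-48 scan.

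The cost is one inexpensive test of a kind the study already uses and a few lines of text. The downside is a small number of missing week-48 retention values, each with a documented reason.
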